1. PROTOCOL SUMMARY / SYNOPSIS

Coordinator	FSNN – Foundation for the Study of Nanoneurosciences and Neuroregeneration
Title	The impact of N-PEP-12 dietary supplementation on attentional performance, cognition, and mental wellbeing of middle-aged and older healthy adults with subjective cognitive function complaints
Study Code	N-HANCE
Study Locations	Single-center
Dietary Supplement	MemoProve/Cebrium
Name of Active Substance	N-PEP-12
Indication	Middle and older age healthy adults
Study Design	Randomized, placebo-controlled, double-blind
Study Duration	Study start: 10/2022 Study end: 06/2024
Sample Size Calculation	
 • K=2 experimental treatments will be included in the trial. • A significance level of $\alpha=0.05$ will be used, in combination with Dunnett's correction. • The standard deviations of the responses will be assumed to be: $(\sigma_0, \dots, \sigma_K)=(1,1,1)$. • The minimum marginal power will be controlled to level $1-\beta=0.9$ under each of their respective least favourable configurations. • The interesting and uninteresting treatment effects will be: $\delta_i=0.5$ and $\delta_0=0$ respectively. • The target allocation to each of the experimental arms will be: the same as the control arm. • Therefore, the realised allocation ratios to the experimental arms are: $(r_1, \dots, r_K)=(1,1)$. • The maximum familywise error-rate is: 0.05. • The minimum marginal power is: 0.9. • The following critical threshold should be used with the chosen multiple comparison correction: 0.028. • 10% adjustment for dropouts 
The total required sample size is: $N=270$. The required sample size in each arm is: $(n_0, \dots, n_K)=(90,90,90)$.
 
Source: Grayling MJ, Wason JMS (2020) A web application for the design of multi-arm clinical trials. BMC Cancer 20:80. DOI: 10.1186/s12885-020-6525-0

Randomization	1:1:1 ratio, 3 blocks, ICH E9

Protocol Number: FSNANO08032022 -2.0 amendment 1 Date: 20032023	
STUDY Code: N-HANCE	Page 6 of 26

CRF	Electronic, open-source, self-developed, ICH E6
Primary Objectives	To assess the efficacy of N-PEP-12 on the Test of Attentional Performance outcomes in healthy middle-aged and older adults at 90 days after baseline.
Secondary Objectives	To assess the efficacy of N-PEP-12 on individual outcomes (cognitive function, functional outcome, mental wellbeing, mood, and quality of life) in healthy middle-aged and older adults at 30, 90 and 180 days after baseline. To assess the efficacy of N-PEP-12 on the Test of Attentional Performance outcomes in healthy middle-aged and older adults at 30 and 180 days after baseline.
Screening Variables	
 • Medical exam • Demographic variables
Primary Variables	Test of Attentional Performance (TAP) Subtests: 
 • Alertness (phasic alertness) • Working Memory (difficulty level 3) • Divided Attention
Secondary Variables	
 • Wechsler Adult Intelligence Scale (WAIS-IV) - Digit Span Forward, Backward (DSF, DSB) • Perceived Stress Scale (PSS) • Brief Mood Introspection Scale (BMIS) • Sleep Quality Scale (SQS) • EQ-5D-5L
Inclusion Criteria	
 • Sign the informed consent form and fully understand the test content, process and possible adverse reactions, and be able to complete the study according to the test plan requirements • Aged ≥ 50 years or ≤ 75 years, male or female (including the boundary value) • Male body weight ≥ 50kg, female body weight ≥ 45kg, and $18.0 \leq \text{BMI} \leq 29.9$ kg/m² • No clinically significant cognitive impairment (MoCA > 25) • Self-reported subjective cognitive complaints • Literacy to complete tests
Exclusion Criteria	
 • History of drug abuse or alcohol abuse (drank more than 14 units / week of alcohol: 1 unit =285ml beer, 25ml spirits or 100ml Wine) • Gastric sleeve patients • History of drug abuse within 5 years prior to screening, or urine drug screening test was positive • Other clinically major diseases, such as decompensated, in the investigator's judgement (such as neuropsychiatric system, cardiovascular system, urinary system, digestive system, respiratory system, metabolic endocrine system, blood system, skin diseases, immune diseases, tumors, etc.) • Participation in another clinical trial within 3 months prior to enrollment • Pre-existing and active major neurological disease • Injury of writing hand influencing cognitive or other outcome measures, in the investigator's judgment.
Visit Schedule	
Visit 1 - Screening Study day 0
 
 • Demographic data • Medical history and risk factors • ICF • Randomization • Primary and secondary outcomes 
Visit 2 - Efficacy Evaluation Study day 30
 
 • Primary Outcomes • Secondary Outcome 
Visit 3 - Efficacy Evaluation Study Day 90
 
 • Primary Outcomes • Secondary Outcome

Protocol Number: FSNANO08032022 -2.0 amendment 1 Date: 20032023	
STUDY Code: N-HANCE	Page 7 of 26

	Visit 4 - Efficacy Evaluation Study Day 180
	
 • Primary Outcomes • Secondary Outcome
Active dietary supplementation arms	N-Pep-12 (45 mg), daily (Day 0-Day 180) N-Pep-12 (90 mg), daily (Day 0-Day 180)
Reference Product	Placebo – Lactose (Day 0-Day 90)

*All treatment cycles and efficacy evaluations will be performed within a window of ± 3 working days

2. INTRODUCTION

2.1 Background Information and Study Rationale

The global older population is growing, particularly in developed countries. The number of people aged 60 and up is expected to reach two billion by 2050, up from 900 million in 2015 (He, Goodkind, & Kowal, 2016). Normal mental performance is a vital aspect of quality of life and wellbeing. With greater longevity and shifting demographics, it is more important than ever to understand the characteristics that enable healthy aging (Simpson et al., 2014) and find solutions that can enhance the cognitive processes and overall mental wellbeing that come with the natural process of aging.

The basic mechanisms involved in attention, perception, memory, and learning are referred to as cognitive functions (Eysenck, 2018). The majority of cross-sectional studies on healthy individuals suggest that attention, working memory, and information processing speed deteriorate gradually between the ages of 20 and 60 (Af, L, Sj, W, & Wt, 2004; Craik & Byrd, 1982; Salthouse, 2009). Moreover, lower cognitive ability and greater decline in cognitive ability predict mortality in older people, even when other biomedical risk factors are controlled for (Batterham, Mackinnon, & Christensen, 2012; Connors, Sachdev, & Kochan, 2015).

N-PEP-12 is a peptide-based nutritional supplement that has been proven in experimental studies and early clinical studies to have neuroprotective and pro-cognitive effects in patients with age-related cognitive impairments (Crook, Ferris, Alvarez, Laredo, & Moessler, 2005; Hutter-Paier, Reininger-Gutmann, Wronski, Doppler, & Moessler, 2015). After only 30 days of a once-daily intervention with 90 mg of N-PEP-12, it was found to considerably improve memory impairment in older persons with subjective memory complaints (Crook et al., 2005). Memoprove and Cebrium are two brands of the chemical that are available in film-coated pills or capsules.

Previous research has found that the peptides in N-PEP-12 exhibit qualities similar to those seen in naturally occurring peptide growth factors, such as increasing neurite outgrowth, improving neuronal survival, and protecting against metabolic stress (Windisch, Hutter-Paier, Grygar, Doppler, & Moessler, 2005). This study's rationale is based on these previously documented properties that have the potential to impact the attentional performance, cognition, and mental wellbeing of middle-aged and older healthy adults with subjective cognitive function complaints.

3. STUDY OBJECTIVES

Protocol Number: FSNANO08032022 -2.0 amendment 1 Date: 20032023	
STUDY Code: N-HANCE	Page 8 of 26

This study shall assess the impact of N-PEP-12 dietary supplementation on attentional performance, cognition, and mental wellbeing of middle-aged and older healthy adults with subjective cognitive function complaints.

3.1 Primary Objectives

To assess the efficacy of N-PEP-12 on the Test of Attentional Performance outcomes in healthy middle-aged and older adults at 90 days after baseline.

3.1.1 Primary Variables

Test of Attentional Performance (TAP) subtests:

- Alertness
- Working Memory
- Divided Attention

3.2 Secondary Objectives

To assess the efficacy of N-PEP-12 on individual outcomes (cognitive function, functional outcome, mental wellbeing, mood, and quality of life) in healthy middle-aged adults at 30, 90 and 180 days after baseline.

To assess the efficacy of N-PEP-12 on the Test of Attentional Performance outcomes in healthy middle-aged and older adults at 30 and 180 days after baseline.

3.2.1. Secondary Variables

- Wechsler Adult Intelligence Scale (WAIS-IV) - Digit Span Forward, Backward (DSF, DSB)
- Perceived Stress Scale (PSS)
- Brief Mood Introspection Scale (BMIS)
- Sleep Quality Scale (SQS)
- EQ-5D-5L

4. STUDY DESIGN

Randomized, placebo-controlled, double-blind

N-PEP-12 groups shall be tested against Placebo. The 3 groups are:

Study Group 1: 45mg N-PEP-12

Study Group 2: 90mg N-PEP-12

Study Group 3: Placebo (Lactose)

The trial will be conducted in a sample of healthy middle-aged and older adults, with subjective cognitive function complaints. The study extends over an observation period of 180 days. Four visits for clinical evaluation are planned as follows:

Visit 1 - (Study day 0) - Screening - will consist of the baseline assessment - demographic data and the patient's medical history and risk factors will be collected. Also, the informed consent will be signed and the patient will be randomized. **Visit 2 - (Study day 30)** will be an efficacy evaluation. Between Visit 1, Visit 2 and **Visit 3 - (Study day 90)** patients shall receive their treatment, based on the group they have been allocated at baseline: Placebo, 45mg N-PEP-12 or 90 mg N-PEP-12. Between Visit 3 and **Visit 4 - (Study day 180)** the patients shall continue the treatment with the two N-PEP-12 groups unchanged and the initial Placebo group receiving 90 mg N-PEP-12.

All treatment cycles and efficacy evaluations will be performed within a window of ± 3 working days.

5. SELECTION AND WITHDRAWAL OF PATIENTS

5.1 Patient Inclusion Criteria

- Sign the informed consent form and fully understand the test content, process and possible adverse reactions, and be able to complete the study according to the test plan requirements
- Aged ≥ 50 years or ≤ 75 years, male or female (including the boundary value)
- Male body weight ≥ 50 kg, female body weight ≥ 45 kg and $18.0 \leq \text{BMI} \leq 29.9$ kg/m²
- No clinically significant cognitive impairment (MoCA > 25)
- Self-reported subjective cognitive complaints
- Literacy to complete tests

5.2 Patient Exclusion Criteria

- History of drug abuse or alcohol abuse (drank more than 14 units/week of alcohol: 1 unit =285ml beer, 25ml spirits or 100ml Wine)
- Gastric sleeve patients
- History of drug abuse within 5 years prior to screening, or urine drug screening test was positive
- Other clinically major diseases, such as decompensated, in the investigator's judgement (such as neuropsychiatric system, cardiovascular system, urinary system, digestive system, respiratory system, metabolic endocrine system, blood system, skin diseases, immune diseases, tumors, etc.)
- Participation in another clinical trial within 3 months prior to enrollment
- Pre-existing and active major neurological disease
- Injury of writing hand influencing cognitive or other outcome measures, in the investigator's judgment.

5.3 Stopping and Discontinuation Criteria

5.3.1 Discontinuation Criteria related to the Study

- Insufficient recruitment
- Continuous serious protocol violation and deviation

Protocol Number: FSNANO08032022 -2.0 amendment 1 Date: 20032023	
STUDY Code: N-HANCE	Page 10 of 26

5.3.2 Discontinuation Criteria related to the Patient

Patients will be informed in the Informed Consent Forms that they have the right to withdraw from the study at any time without prejudice, and that they may do so at the discretion of the Investigator / Coordinator. The withdrawal/study termination page in the CRF must be completed whenever a patient drops out or is pulled from the study. In the withdrawal section, the Investigator should record the date of the withdrawal, the person who initiated the withdrawal, and the reason for the withdrawal. To finish evaluations and collect any outstanding data and research materials, reasonable efforts should be taken to reach any patient who went missing during the study for follow-up.

Withdrawn by the Investigator due to:

- Serious Adverse Drug Reaction
- Lack of efficacy
- Consent withdrew
- Administrative reasons

The patient or his/her representative requested withdrawal due to:

- An Adverse Event for which the Investigator did not consider removal from the study
- Perceived insufficient therapeutic effect.
- Withdrawal of consent for any other reason (data recorded until withdrawal will be kept in the database if not explicitly denied by the patient)

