Missing data of the type 'missing completely at random' (MCAR), which in principle will not bias the results; the analysis procedure should be able to cope with partially missing data of such a type. In many studies this type of data is treated by LOCF replacement (Last Observation Carried Forward) as far as there exist follow-up measurements at previous visits.

In a study like the one planned there might also be informatively missing data (missing not at random, MNAR): participants of the study died or are unable to complete the tests because of brain-related impairment. Neglecting these missing data might introduce bias.

In order to identify each type of missing data, outcome scales will be coded for every patient and visit according to the following scheme:

- 1 = valid (complete task)
- 2 = unable to complete (TBI-related neurological reason) [describe reason]
- 3 = not completed (different reasons, not TBI related) [describe reason].

For outcome scales with code "2" a worst rank imputation will be introduced for the corresponding patients since these data are informatively missing (missing not at random, MNAR). These missing data are replaced by the worst possible score of the corresponding outcome scale.

For outcome scales with code "3" a LPCF replacement will be introduced (Last Percentile Carried Forward) as far as previous follow-up evaluations exist. This method carries forward the actual status information of

Protocol Number: FSNANO08032022 -2.0 amendment 1 Date: 20032023	
STUDY Code: N-HANCE	Page 19 of 26

the patient population, using the percentile value with back transformation to raw scale, instead of the last value carried forward. This approach was recently developed and recommended by O’Brien, Zhang and Bailey (2005) for the analysis of data from chronic, progressive diseases such as dementia. According to their simulation study the calculated estimators should be negligibly biased by missing data. If no general change of patients over time occurs the method is more or less identical with LOCF (Last Value Carried Forward), if change occurs bias is minimized. If no previous follow-up measurement exists, the outcome scale remains missing.

Study populations and protocol violations

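### Participants withdrawn for lack of effect have no stated Day 90 assessment, and the imputation rule then fills their primary score from their Day 30 standing

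*Protocol*

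**What the plan says.** Protocol Section 5.3.2 lists "Lack of efficacy" among the investigator's reasons for withdrawal and "Perceived insufficient therapeutic effect" among the participant's. A CRF page with date, initiator and reason "must be completed whenever a patient drops out or is pulled from the study". The only follow-up effort named is that "reasonable efforts should be taken to reach any patient who went missing during the study for follow-up". Nothing is said about assessing a participant who was withdrawn and can still be reached.

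Section 12 codes each outcome scale at each visit. Code "2 = unable to complete (TBI-related neurological reason") is treated as informative and receives the worst possible score. Code "3 = not completed (different reasons, not TBI related") takes everything else, and for it "a LPCF replacement will be introduced (Last Percentile Carried Forward) as far as previous follow-up evaluations exist". Without an earlier follow-up value the score stays missing. The same section warns that ignoring informatively missing data may cause bias.

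**The concern.** Two of the listed reasons for leaving relate to the quantity the trial measures. The coding scheme has no place for them except the residual category, whose imputation assumes that a participant's rank at the last visit still holds at the next.

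The primary objective in Section 3.1 concerns Day 90, while the background in Section 2.1 cites a benefit after 30 days at 90 mg. If the effects at the two visits differ, carrying Day 30 ranks forward blends the earlier answer into the later one. An assessment that was never made cannot be recovered by any later analysis plan, so what is collected after withdrawal has to be settled in the protocol.

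**Working it through.** **Following the rule through**

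- Section 10.1 has visits at Days 0, 30, 90 and 180, so Day 30 is the only follow-up before Day 90.
- A participant withdrawn for lack of effect between Days 30 and 90 has no TBI-related reason. Code 2 does not apply and code 3 does.
- Code 3 triggers LPCF (last percentile carried forward), so the Day 90 score is the Day 90 value at that participant's Day 30 percentile.
- Section 12 uses the ITT set for all efficacy analyses. It requires one post-baseline primary observation, so this participant is in it with an imputed score. Someone who leaves before Day 30 stays missing and falls outside the ITT set.

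**Inputs for the size**

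- From Section 12: 90 per arm, SD 1, design effect 0.5 SD, threshold 0.028, 10% dropout allowance.
- Assumed: correlation 0.7 between Days 30 and 90; everyone below the placebo 5th or 10th percentile at Day 30 withdraws; percentiles pooled over arms; one dose against placebo; higher score better (signs reverse for reaction times).

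**The plan's own figure.** One-sided Dunnett with two comparisons (correlation 0.5) gives c = 1.916 and p = 0.0277, which rounds to the stated 0.028. Then n = 2 × ((1.916 + 1.282)/0.5)² = 81.8, so 82 per arm and 246 in total; 246 × 1.1 = 270.6 against the stated 270. The two-sided version gives c = 2.212, p = 0.0270 and 98 per arm before dropout, which does not fit. The threshold is therefore read as one-sided.

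**Shares withdrawn.** Placebo: 5% or 10% by construction. Active arm with a 0.5 SD effect at Day 30: Φ(-1.645 - 0.5) = 1.6% or Φ(-1.282 - 0.5) = 3.7%. At the 10th percentile the average over the two arms is (10 + 3.7)/2 = 6.9%.

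**Simulated bias in the Day 90 difference under LPCF**

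| True effect, Day 30 then Day 90 (SD) | Bias (SD) |
|---|---|
| 0.5 then 0 | +0.02 to +0.05 |
| 0.5 then 0.5 | about 0 to +0.02 |
| 0.25 then 0.5 | about -0.01 |
| 0 then 0.5 | -0.02 to -0.05 |
| 0 then 0 | none |

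In the first row one-sided rejection is about 0.036 to 0.054 against 0.028; in the last row it stays at about 0.028. The spread comes from the withdrawal percentile and from how the percentile is turned back into a score. If only observed Day 90 scores are used, as a real analysis must, the first row gives +0.023 SD (5th percentile) and +0.035 SD (10th). The upper end uses the full Day 90 distribution.

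**Random dropout for comparison.** If a fraction d leaves at random, the imputed participants contribute the Day 30 difference in place of the Day 90 one, so bias ≈ d × (Day 30 effect - Day 90 effect). For 0.5 then 0:

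- d = 6.9%: 0.069 × 0.5 = 0.034 (simulated 0.032)
- d = 10%: 0.10 × 0.5 = 0.05 (simulated 0.048)

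**Another withdrawal rule.** If half of those with the poorest change from baseline leave (10% of placebo, 3.5% of active), the first-row bias is 0.06 SD and rejection 0.06. At 20% of placebo and 9% of active it is 0.09 SD and 0.10, but 20% is twice the planned dropout.

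**The case against.** The strongest reply is that the protocol is silent here, not wrong. Nothing in it forbids a Day 90 TAP after withdrawal for lack of effect. A reader might infer that such data are discarded from the statement that "data recorded until withdrawal will be kept in the database if not explicitly denied by the patient", but that parenthesis belongs only to the item on withdrawing consent for other reasons. That reply stands; the point rests on the missing provision alone.

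The reason must be described for each code, so these cases could be separated later, and sensitivity analyses may properly sit in the SAP. This is also true. Separating the cases does not supply the missing score, however, and the protocol already commits code 3 to LPCF.

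A reader might also infer that an early benefit will be carried into Day 90 and inflate the result. That is not supported. The sign depends on the course of the effect, and a late-appearing effect is understated. The people withdrawn also carry low ranks, not a benefit; the difference arises from unequal numbers and ranks between arms.

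Nor is outcome-driven withdrawal the whole cause, since random dropout gives a similar bias. The simulated withdrawals depend only on the observed Day 30 score, so they do not demonstrate loss that is informative given the observed data. Finally, the cited 30-day benefit concerns memory at 90 mg, not TAP or 45 mg, so a 0.5 SD effect at Day 30 is an assumption, and so is its disappearance.

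**Conclusion.** The point holds as a gap in data collection joined to an ill-fitting missing-data code. Sections 5.3.2 and 12 together send effect-related withdrawals to a Day 90 value taken from Day 30.

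At withdrawal rates within the planned 10%, the bias is at most about 0.05 SD in either direction under the main assumptions (0.06 SD under the alternative withdrawal rule), roughly a tenth of the 0.5 SD design effect. It vanishes when there is no effect at either visit, so it does not inflate error under that null. The figures rest on the assumed correlation of 0.7 and on assumed withdrawal rates. The protocol gives no dropout rate by reason and no definition of lack of efficacy, so the true size is uncertain.

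This is a worthwhile, inexpensive improvement and not a threat to the trial's validity. Whether participants should be withdrawn for lack of efficacy is a clinical rule and is not judged here. Day 90 is taken as the primary time point from Section 3.1; Section 12 names Days 90 and 180, and the two must be reconciled.

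**What to change.** Leave the withdrawal reasons as they are and reconcile Sections 5.3.2 and 12.

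- **Section 5.3.2:** state that a participant who stops the product but consents to assessment completes the remaining scheduled TAP visits, and that these data enter the ITT analysis.
- **Section 12, coding:** give withdrawal for lack or perceived lack of effect its own missing-data code outside LPCF. Reword the TBI-related codes at the same time, since they do not fit healthy adults.
- **Section 12, analysis:** handle what is still missing with a likelihood-based or multiple-imputation analysis that uses the Day 30 score and is specified before unblinding. The protocol names no such model at present.

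The cost is one amendment and one CRF code; the visits are already in the schedule. The data-collection part helps only participants who have yet to reach Day 90, whereas the coding and analysis parts can be settled at any time before unblinding. The downside is that some observations will be off product, so the estimate answers a treatment-policy question, and the protocol should say so.

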5.4 Randomisation, Blinding and Unblinding

This study will be conducted under double-blind conditions in order to keep investigators, other study personnel, and patients unaware of treatment allocation. A unique randomization number will be assigned to patients who fulfill the inclusion and exclusion criteria (patient number). This number is the next available randomization number in ascending order from 001 to, for example, 999 of a predefined randomization plan, and it identifies the treatment assigned to a unique patient in a double-blind manner, from a random list generated in advance by a biometrician chosen by the coordinator. Patients will be randomly allocated the study groups in a 1:1:1 ratio.

A sealed random code list and sets of sealed envelopes are prepared. Based on the random list sealed, opaque randomization/emergency envelopes will be provided as follows:

- To the study center to break blinding if reasonable suspicion of harm to the patient exists
- To the person assigned to prepare the ready-to-use-infusion
- To the study coordinator

When the randomization envelopes are opened, the person who opened them will date (day, hour) and sign them. Any premature unblinding of the Investigational Product should be noted as soon as possible and explained to the Coordinator. The complete study will be unblinded after the database is closed and the analysis populations are identified.

